3.3. Targeted Follow-Up Questionnaire (TFUQ) Report

As documented in protocol and elsewhere in this RAP, this study includes a Targeted Follow-Up Questionnaire (TFUQ) for subjects with sexual function related adverse events leading to study withdrawal. Using the TfuQ, subjects will be followed for up to 6 months after the last dose of study drug. It is anticipated that the final TfuQ data component will be included in the above referenced primary database freeze.

However, if there are ongoing TfuQs at the time of primary database freeze, and anticipated follow-up and receipt of these data would create a delay in analyzing and reporting the study results then the primary freeze may occur with exclusion of outstanding TfuQ data. Thereafter, a secondary database freeze will occur in terms of newly finalized and recorded TfuQ data (since primary freeze). The decision to perform a secondary freeze will be made soon after last subject last visit milestone by Project Team with input from Data Management, International Regulatory Affairs, Clinical Statistics, Clinical Development, and Clinical Operations. This secondary freeze will be in terms of datasets containing the actual TfuQ and as well as any TfuQ-related datasets. Only TfuQ-related tabular summaries and listings (related to newly frozen datasets) will be updated with the secondary freeze. TfuQ-related summaries and listings for this secondary freeze will be referred to as 'TfuQ Report'.

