8.2.2. Adverse Events

Adverse events (AEs) will be coded using the MedDRA (Medical Dictionary for Regulatory Activities) coding dictionary. As specified in the protocol, disease related events will not be reported as AEs or serious adverse events (SAEs) unless the investigator assesses the event as more severe than expected for the subject's condition. A mapping of the MedDRA primary system organ class and preferred term to which each verbatim term has been coded will be provided in a listing.

Adverse events (AEs) are to be recorded on the electronic case report form (eCRF) from the start of the placebo run-in phase study treatment until the end of the two year study period. Serious AEs (SAEs) are to be recorded over the same time period as non-serious AEs. However, any SAEs assessed **as related** to study participation or related to a GSK concomitant medication, will be recorded from the time a subject consents to participate in the study up to the end of the two year study period. After discontinuation of study treatment, the investigator will monitor all AEs/SAEs that are ongoing until resolution or stabilization of the event or until the subject is lost to follow-up. Investigators are not required to actively seek information on adverse events occurring after the follow-up contact, but may report any adverse event that they believe may be related to investigational product regardless of when the event occurs. Adverse events summaries will include non-serious as well as serious AEs.

Subjects with sexual function related adverse events leading to study withdrawal, will be followed up for up to 6 months after the last dose of study drug using the sexual function Targeted Follow-Up Questionnaire (TFUQ).

If an AE occurs which, in the investigator's judgment, is possibly related to suicidality, a Possible Suicidality-Related Adverse Event (PSRAE) form should be completed by investigators or their designated staff.

Each AE will be categorized into the following periods according to its onset date: pretreatment, post-randomization, on-treatment, post-treatment. These periods are not mutually exclusive and an AE could be categorized into more than one period. The definitions of these categories are provided in [Appendix 8: Adverse Event Time Periods and Special Adverse Event Definitions](#).

Pre-treatment AEs will not be summarized; they will be included in the AE listing specified later in this section.

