The time to first onset in days will be summarized by treatment group as a continuous variable as well as by time period of onset. In addition, time to first adverse event of special interest will be summarized by treatment group using estimates calculated by the Kaplan-Meier method and displayed graphically as Kaplan-Meier curves. Time to resolution for the first event in days will be summarized by treatment group.

Duration of adverse events of special interest will be summarized by treatment group for uncensored values, censored values, and all values. It is recognized that summary statistics such as means and medians involving censored values will be biased (low).

The number of sexual and breast adverse events leading to study withdrawal, as well as the number and percentage of subjects reporting at least one such sexual and breast adverse event will be provided for all event types and also by event type for each treatment group.

Resolution status at end of study (resolved, not resolved) and time from treatment stop date to AE resolution will be summarized by treatment group for the sexual and breast adverse events leading to study withdrawal and not resolved at Month 24 / End of Treatment visit.

Listings of sexual and breast adverse events of special interest will be provided. A listing of sexual and breast adverse event status data will be provided.

A listing of the TFUQ data for sexual and breast adverse events will be provided.

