
From the above standards and principles as well as to be aligned with historical reporting for this compound and indication, the key reporting standards to be applied are:
 
 All data will be reported according to the actual treatment the subject received unless otherwise stated. Within listings, numeric data will be reported at the precision collected on the eCRF. The reported precision from non eCRF sources will follow the IDSL statistical principles but may be adjusted to a clinically interpretable number of decimal places. Within tabular summaries, the minimum and maximum values are presented with the same 	

Reporting Standards

number of decimal places as the raw data collected on the eCRF. The mean and percentiles (e.g. median, Q1, and Q3) are presented using one additional decimal place. The standard deviation and standard error are presented using two additional decimal places.

- Continuous variables (e.g., age) will be summarized using the number of observations (n), mean, standard deviation (SD), median, minimum, and maximum.
- Categorical variables will be summarized using the number of subjects (n) and percentage (%) in each category.
- P-values greater than 0.10 will be reported to two decimal accuracy. P-values less than or equal to 0.10 will be reported to three decimal accuracy. P-values less than 0.001 will be reported as '<0.001'.
- Applicable safety analysis and reporting definitions and presentations within "Program Safety Analysis Plan ([PSAP](#)) for GI198745 (dutasteride) and GSK2285985 (fixed dose combination of dutasteride [GI198745] and tamsulosin [GI138525])" will be referenced; any deviations will be noted within this RAP.

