For computing AE duration, partial AE start and end dates will be imputed as previously described, and events with completely unknown (missing) end dates will be censored at the latter of the following two dates: date of last clinic visit, latest AE start date. AE duration is the total number of non-overlapping days for all events per subject, and will be considered censored if any contributing event is censored.

Time to death is defined as (date of death – treatment start date +1). For subjects who do not experience death, time to death is censored at the date of last clinic visit (if missing,

the subject will be censored at the treatment start date).

Special interest adverse events, including MedDRA preferred terms and codes, are presented below in [Table A](#)-[Table D](#):

Table A: Sexual and Breast Adverse Events of Special Interest

Table B: Prostate Cancer Adverse Events of Special Interest

Table C: Cardiovascular Adverse Events of Special Interest

Table D: Infrequent Tier 1 Adverse Events of Special Interest

Table A. Sexual and Breast Adverse Events of Special Interest: MedDRA Preferred Terms and Codes		
Special Interest Event	MedDRA Preferred Term	PT_Code
Altered (Decreased) Libido	Sexual dysfunction	10040477
	Male sexual dysfunction	10057672
	Libido decreased	10024419
	Loss of libido	10024870
	Libido disorder	10061221
Impotence	Erectile dysfunction	10061461
	Organic erectile dysfunction	10052004
	Disturbance in sexual arousal	10058929
	Psychogenic erectile dysfunction	10052005
Ejaculation Disorders	Ejaculation delayed	10014325
	Ejaculation disorder	10014326
	Ejaculation failure	10014328
	Retrograde ejaculation	10038967
	Anorgasmia	10002652
	Orgasm abnormal	10031085
	Premature ejaculation	10036596
	Male orgasmic disorder	10025513
	Orgasmic sensation decreased	10052449
	Semen volume decreased	10039944
Breast Disorders	Breast hyperplasia	10006256
	Breast enlargement	10006242
	Gynaecomastia	10018800
	Nipple disorder	10029417
	Breast engorgement	10006240
	Breast swelling	10006312
	Breast pain	10006298
	Breast tenderness	10006313
	Nipple pain	10029421
	Nipple swelling	10058680
Breast Disorders: Breast Enlargement	Breast discomfort	10049872
	Breast hyperplasia	10006256
	Breast enlargement	10006242
	Gynaecomastia	10018800
	Nipple disorder	10029417
	Breast engorgement	10006240
Breast Disorders: Breast Tenderness	Breast swelling	10006312
	Breast pain	10006298
	Breast tenderness	10006313
	Nipple pain	10029421
	Nipple swelling	10058680

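### Duration of special-interest adverse events is summarised by statistics that run low in every row, and the censoring date in Appendix 8 ignores later knowledge that an event is still ongoing

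*SAP*

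**What the plan says.** SAP 8.2.4.3 (Sexual and Breast Tier 1 Adverse Events of Special Interest) sets the display: "Duration of adverse events of special interest will be summarized by treatment group for uncensored values, censored values, and all values". The next sentence is the admission: "It is recognized that summary statistics such as means and medians involving censored values will be biased (low". Section 11.5.2 makes mean and median standard for this kind of variable: "Continuous variables (e.g., age) will be summarized using the number of observations (n), mean, standard deviation (SD), median, minimum, and maximum". Sections 8.2.4.4 and 8.2.4.5 reuse the format for prostate cancer and cardiovascular events.

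Appendix 8 (11.8) defines duration as a man's total non-overlapping days over all his events of the type. It sets the censoring date as follows: "events with completely unknown (missing) end dates will be censored at the latter of the following two dates: date of last clinic visit". The other of the two candidates is the onset of the man's most recent adverse event. The total "will be considered censored if any contributing event is censored".

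Follow-up can run past that date. For sexual-function adverse events leading to study withdrawal, section 3.3 says of the Targeted Follow-Up Questionnaire (TFUQ): "Using the TfuQ, subjects will be followed for up to 6 months after the last dose of study drug". Section 8.2.2 repeats this and also has investigators monitor ongoing adverse events after treatment stops, until they resolve or stabilise or the man is lost to follow-up.

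The same part of 8.2.4.3 names Kaplan-Meier for time to first onset. It also plans time to resolution of the first event in days, but gives no method and no rule for unresolved events.

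**The concern.** A reader of these tables wants to know how long a sexual or breast event lasts and whether that differs by arm. None of the three rows estimates this. The censored row and the all-values row treat a lower bound as a duration. The uncensored row is selected for short events. All err in the reassuring direction, and the error grows with the true duration, so a longer-lasting effect in one arm would look closer to the other arm than it is.

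The censoring rule makes this worse in a way that a change of estimator alone would not repair. Whether later follow-up contributes depends on what it found: a resolution supplies an end date, while a finding that the event continues supplies nothing. For acute urinary retention and BPH-related surgery, section 8.1.5 lets the last successful telephone contact extend the censoring date. Appendix 8 has no counterpart for adverse event duration.

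**Working it through.** The plan states no number on this point, so there is no figure to reproduce. The check has two parts. All durations, onset patterns and withdrawal times below are assumptions, not figures from the plan.

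**A. The three-row summary**

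Inputs: one event per man; exponential duration with rate λ = ln 2 / (true median); onset uniform over the 104-week treatment period (104 × 7 = 728 days); censoring at day 728. Time available after onset is then uniform on 0 to 728.

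- All-values median m: P(observed time > m) = exp(−λm) × (1 − m/728) = 0.5.
- Censored share: [1 − exp(−728λ)] / (728λ).
- Uncensored median u: solves F(u) = F(728)/2, where F(t) is the integral from 0 to t of λ·exp(−λs)·(1 − s/728) ds.

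Worked case, true median 365: λ = 0.6931/365 = 0.001899. At m = 198, exp(−0.376) × (1 − 0.272) = 0.687 × 0.728 = 0.500. The censored share is (1 − 0.251)/1.382 = 54%.

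| True median (days) | Censored | All-values median | Shortfall | Uncensored median |
|---|---|---|---|---|
| 30 | 6% | 28 | 6% | 28 |
| 90 | 18% | 76 | 16% | 73 |
| 180 | 34% | 129 | 28% | 115 |
| 365 | 54% | 198 | 46% | 155 |
| 730 | 72% | 261 | 64% | 181 |

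Shortfall is 1 − (all-values median / true median). Simulation with 400,000 events per scenario agrees to within about 1 day. In simulation Kaplan-Meier recovers true medians of 3, 6 and 12 months. In the 730-day case survival at day 728 is exp(−0.691) = 0.501, so the Kaplan-Meier median is not reached.

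**B. The censoring rule**

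Inputs: exponential duration; withdrawal, taken as the last clinic visit, uniform 1 to 3 months after onset; follow-up for 6 further months. Under the Appendix 8 rule, a resolution within those 6 months is a completed duration, and an event unresolved at their end is censored at the last clinic visit (no later adverse event assumed). Simulation, 400,000 events:

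| True median (months) | Unresolved at last contact | All-values median, plan's rule | Kaplan-Meier, plan's rule | Kaplan-Meier, censored at last contact |
|---|---|---|---|---|
| 3 | 16% | 2.2 | 2.7 | 3.0 |
| 6 | 40% | 2.3 | 3.9 | 6.0 |

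Kaplan-Meier on the plan's censoring date is still low, because the men set back to an early date are exactly those known to be unresolved. The estimator and the date must change together. The other limb of the rule, the latest adverse event start date, does not help: a new adverse event does not show when the unresolved one was last known to be ongoing.

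**The case against.** The strongest reply is that the plan hides nothing and reports persistence elsewhere. The direction of bias is stated, and censored and uncensored values are shown apart. Section 8.2.4.3 also tabulates outcome and on- or off-therapy resolution of the first event. For sexual and breast events that led to withdrawal and were unresolved at Month 24 or end of treatment, it adds resolution status at end of study and time from treatment stop to resolution (Tables 3.49 to 3.53). TFUQ data are listed. These are descriptive safety displays with no test attached. Much of this stands. A count of resolved against unresolved is free of the bias in the means and medians, and a reader who inferred that persistence goes unreported would be wrong. Two gaps remain: the time from treatment stop exists only for men who resolved, and the admission does not reach the uncensored row.

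The second reply concerns size. Part A models one event per man, whereas Appendix 8 totals days over all a man's events, and the true medians are assumed. This stands too: 198 days is not a prediction of what the table will show, and for events of about a month the loss is about 6%.

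The third concerns scope. The TFUQ is described for sexual-function events leading to withdrawal. Nothing says it covers breast events or men who stayed in the study. For those, the only follow-up that could be unused is the general monitoring in 8.2.2.

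**Conclusion.** The point holds as a defect in a descriptive safety analysis. The primary efficacy test is untouched. All three duration rows run low, and the Appendix 8 date adds bias by using later follow-up when it shows resolution and not when it shows the opposite.

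The direction is certain for the all-values and uncensored rows whenever some events are censored. The size is not known. Under Part A's assumptions the all-values median falls short by 28%, 46% and 64% at true medians of 180, 365 and 730 days, and by little for short events. Part B further assumes that resolutions found after the last visit are entered as end dates, which the plan permits but does not spell out.

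A reader might also infer that the comparison between arms will be distorted by a known amount. The documents do not support that: they give no durations or resolution rates by arm. What follows is only that the bias grows with true duration.

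**What to change.** 1. In 8.2.4.3, and so in the formats that 8.2.4.4 and 8.2.4.5 borrow, add Kaplan-Meier time from onset to resolution of the first event by arm: proportion unresolved at 3, 6 and 12 months with 95% confidence intervals, the median if reached, and the number unresolved. This also supplies the missing method for the planned time to resolution of the first event.
2. In Appendix 8, censor an unresolved event at the last date its status was known, counting TFUQ and other post-visit contacts.
3. Keep total-days duration only if it is labelled as observed follow-up.

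The costs are small but not nil. There is extra programming in each event category. A first-event analysis does not capture recurrent burden, which is the reason to keep a labelled total. Section 3.3 allows the primary freeze to go ahead without outstanding TFUQ data and then updates only TFUQ-related displays, so the new tables must be added to that set.

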8.2.4.4. Prostate Cancer Tier 1 Adverse Events of Special Interest

Prostate cancer will be defined as an adverse event of special interest. MedDRA preferred terms and codes included in this special interest adverse event are defined in [Appendix 8, Table B](#). Prostate cancer events will be summarized separately following the same format done for sexual and breast special interest AEs described above. Time to first event for prostate cancer events will be summarized separately by treatment group using estimates calculated by the Kaplan-Meier method and displayed graphically as Kaplan-Meier curves.

Listings of prostate cancer adverse events of special interest will be provided.

8.2.4.5. Cardiovascular Tier 1 Adverse Events of Special Interest

Cardiovascular adverse events of special interest will be defined as those included in the following six categories: acute coronary syndrome, ischemic coronary artery disorders/atherosclerosis, ischemic cerebrovascular events, cardiac failure, cardiac arrhythmias, and peripheral vascular disease. MedDRA preferred terms and codes included in these special interest adverse events are defined in [Appendix 8, Table C](#). Total number of cardiovascular events as well as the number and percentage of subjects experiencing cardiovascular events will be provided by treatment group. Each category of cardiovascular events, and all cardiovascular events as one additional category, will be summarized separately following the same format done for sexual and breast special interest AEs described above. Time to first cardiovascular adverse event of special interest will be summarized by treatment group using estimates calculated by the Kaplan-Meier method and displayed graphically as Kaplan-Meier curves.

Listings of cardiovascular adverse events of special interest will be provided.

Note: The protocol Section 7.4.2.2 (Cardiovascular Events) indicates additional data collection required for some cardiovascular events and procedures; these data will be output in data listings. Cardiovascular events in protocol Section 7.4.2.2 are not the full set of cardiovascular adverse events defined in this RAP section.

8.2.4.6. Infrequent Tier 1 Adverse Events of Special Interest

Infrequent Tier 1 adverse events of special interest will be defined as those included in the following categories:

- Breast cancer
- Potential for decreased male fertility due to effects on sperm/semen characteristics
- Interference with formation of external genitalia in a male fetus if a woman carrying a male fetus is exposed to dutasteride

- Hair changes
- Allergic reactions
- Depressed mood
- Testicular pain and swelling
- Intraoperative floppy iris syndrome
- Orthostasis
- Priapism
- Stevens-Johnson syndrome
- Atrial fibrillation, tachycardia, arrhythmias

MedDRA preferred terms and codes included in these special interest adverse events are defined in [Appendix 8, Table D](#). Total number of infrequent Tier 1 events as well as the number and percentage of subjects with infrequent Tier 1 events will be provided by treatment group.

Listings of infrequent Tier 1 adverse events of special interest will be provided.

8.2.5. Pregnancies

A listing of subjects whose female partner become pregnant during the study will be provided if there are any such subjects.

8.2.6. Clinical Laboratory Assessments

Clinical chemistry and hematology parameters are evaluated from samples scheduled at the first screening visit (1a) and at each Month 12 and Month 24 (or end of treatment) visits. The following tests will be performed:

Clinical Chemistry (serum): Alkaline phosphatase (ALP), alanine aminotransferase (ALT), aspartate aminotransferase (AST), total bilirubin, total protein, sodium, potassium, albumin, glucose, creatinine, UREA/BUN (blood urea nitrogen)

Hematology: Hemoglobin, platelet count, white blood cell count (WBC), red blood cell count (RBC)

For purposes of statistical analyses the baseline value of a parameter for each subject will be defined as the latest laboratory test value on or before the start of the randomized treatment for that subject.

The final value of a parameter for each subject is defined as the latest post-baseline value available in the study for that subject. A summary of parameter values, including the baseline and final value, will be provided by treatment group and scheduled visit. A summary of change from baseline in parameter values, including the final value, will also be provided by treatment group and scheduled visit.

A laboratory value that is on or within the normal range is considered normal. A laboratory value that is above the upper limit of the normal range is considered high abnormal. A laboratory value that is below the lower limit of the normal range is considered low abnormal.

The number and percentage of subjects with an abnormal laboratory value at baseline among subjects with a baseline laboratory value and at least one post baseline laboratory value will be provided by treatment group and by parameter. The number and percentage of subjects will be summarized by treatment group for each laboratory test for the following shift categories:

- Normal at baseline to abnormal at any time post-baseline
- Normal at baseline to high at any time post-baseline
- Normal at baseline to low at any time post-baseline
- Normal or low at baseline to high at any time post-baseline
- Normal or high at baseline to low at any time post-baseline

Laboratory data transitions from baseline to final assessment will be summarized for each parameter according to the following categories:

- Decrease: High to Low, Normal to Low, High to Normal
- No Change: Low to Low, Normal to Normal, High to High
- Increase: Low to Normal, Normal to High, Low to High

The threshold laboratory values are defined in terms of a multiplicative factor of the testing laboratory's normal range. A laboratory value that is above the upper limit factor multiplied by the upper limit of the normal range is considered a high threshold value. A laboratory value that is below the lower limit factor multiplied by the lower limit of the normal range is considered a low threshold value. Refer to [Appendix 9](#) for a listing of the laboratory threshold factors.

The number and percentage of subjects with a threshold laboratory value at baseline among subjects with a baseline laboratory value and at least one post baseline laboratory value will be provided by treatment group and by parameter. Subjects with threshold values any time post-baseline with a non-threshold baseline laboratory value and at least one post-baseline laboratory value will also be summarized by treatment group and by parameter.

Listings of hematology and clinical chemistry data will be provided, along with listings of hematology and clinical chemistry data exceeding threshold.

The protocol defines possible drug-induced liver injury with hyperbilirubinaemia, for laboratory assessments planned in this study, as:

$$\text{ALT} \geq 3 \times \text{ULN} \text{ and } \text{Bilirubin} \geq 2 \times \text{ULN}$$

A listing of subjects meeting this defined liver function abnormality along with the corresponding data will be provided. If no subjects meet the defined criteria, a listing (page) will be produced indicating that no subjects met the criteria.

A blood draw for HBsAg and Hepatitis C Antibody is scheduled for Visit 2 (baseline). These measurements will be included in a data listing.

